
The following documents are currently attached to this item:

There are no documents attached for this item.

Analysis Plan

Analytic Methods General: The statistical analysis will proceed in three stages: First, we will check the data quality and carry out descriptive analyses of demographics and key outcome variables. Next, we will assess preferences using conjoint analysis and inferential analysis. For continuous outcome variables, we will check for homogeneity of errors using spread-vs.-level plots and will consider transforming variables that either are highly skewed or have variance that depends strongly on the mean. We will use methods based on general linear model (univariate and repeated-measures ANOVA, mixed models) to analyze uncensored continuous outcomes, such as generic and prostate-specific HRQoL, psychological wellbeing and satisfaction with care. For potentially censored outcome variables such as time to PSA recurrence, we will use Kaplan-Meier curves and Cox proportional hazard models. Poisson regression (zero-inflated) will be used for count data. We will use Bonferroni correction for multiple testing. We will use propensity-score and instrumental variable approach to minimize observed and unobserved bias within groups (i.e. intervention group and usual care control group). **Missing Data:** We will attempt to prevent missing data by ensuring that data collection is as complete as possible. Should there be substantial missing data, however, we will employ analysis and imputation methods to reduce bias and increase efficiency [279-282]. Based on the proportion of missing data, we will use complete-case analysis, or explore available techniques, such as standardized score imputation, simple means imputation, maximum likelihood model-based imputation, data augmentation, etc. [281]. When data are evidently non-missing at random, we will conduct explicit non-ignorable modeling and sensitivity analysis [278]. **Propensity score matching:** In observational studies, comparisons between treatment groups that do not adjust for factors associated with treatment choice may be biased. Propensity score technique offers a highly practical approach to address such bias [283]. Here, the probability of each participant being in the treatment arm (i.e., the propensity score), is estimated. Participants are sorted by their propensity scores; the sample is divided into strata based on estimated scores, the treatment effect within each stratum estimated and overall estimate computed by aggregating across strata in a weighted analysis. When the model for predicting treatment status includes all relevant covariates, within strata treatment groups will be balanced on all predictors and the overall comparison of treatment arms will have substantially lower bias. We will use a model relating PCa treatment (RP, RALP, EBRT, PT, BT or AS) to baseline factors [283-284]. To study the extent to which treatment groups are now matched, we will compare t-statistics for these covariates before and after adjusting for propensity score. This will be done separately for intervention group and usual care controls. **Instrumental variable analysis:** Another limitation of observational research is the strong potential for confounding bias, due to differences in comparison groups that are not reflected in the data (i.e., unobserved bias). The instrumental variable (IV) approach is useful in reducing this bias. This technique uses one or more observable factors that influence outcome only indirectly (the IV). This allows one to mimic randomization with different likelihoods of receiving a particular treatment [227, 285-291]. Physicians play an important role in patients treatment choice- a majority of the PCa patients report that their physicians recommendation was the most important factor in their treatment choice [11-12, 37-46, 51, 55-56, 60-64]. We will use specialty of the first physician (urologist, urologic oncologist, oncologist, radiation oncologist) who the patient saw during PCa diagnosis as an IV. We will explore other potential IVs, such as absolute distance between patients residence to the hospital where they will receive care (Hospital of University of Pennsylvania, Presbyterian Medical Center, PVAMC, Pennsylvania Hospital, or Fox-Chase Cancer Center). Validity of the IV(s) is assessed as following. First, we will use Pearsons correlation coefficient to examine the correlation between IV, primary exposure (treatment) and outcomes. We will then perform a partial F-test using a linear regression where treatment group is regressed on physician specialty along with patient attributes. For a valid IV, test statistic should be very high (e.g., physician specialty will strongly predict treatment after adjusting for covariates). Next, we will perform a partial F-test using a linear probability model in which HRQoL outcomes are regressed on specialty and patient demographic and clinical variables. For an IV to be valid, this test statistic should be very low. Finally, we will compare observable attributes across patient groups cared for by different physician specialty (initial). For the IV be valid, these groups should have comparable observable attributes. **Phase 1 Focus group analysis-development of conjoint task instrument:** The goal of focus groups is to identify attributes of PCa treatment that are most salient to localized PCa patients. This process includes following steps: (1) identifying and defining attributes; (2) assigning attribute levels; and (3) creating scenarios and choice sets. Attributes will be defined based on input from patient focus groups, literature, our prior research, and prior physician focus group. Once an attribute and its extreme values are defined, we will assign them appropriate levels. A large number of possible combinations of attributes and levels will preclude

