Potential benefits: Prostate cancer is a slow progressing, chronic and debilitating disorder that substantially limits quality and quantity of life for nearly millions of Americans. There exists significant ambiguity regarding the best treatment for prostate cancer for a particular patient since prostate cancer treatments involve inherent tradeoffs between quantity and quality of life. Thus, the treatment for

prostate cancer presents a clinical dilemma even with perfect data. Clinically similar patients can receive different treatments, given that their preferences may differ. The results of this study will add new knowledge regarding the extent to which the newly diagnosed prostate cancer patients prefer to be involved in decision making, the extent to which prostate cancer patients perceive decision conflict, preferences and the role of demographic and clinical characteristics in relation to involvement in decision making and decision conflict. Evidence shows that there are substantial opportunities to improve the care delivered to prostate cancer patients by analyzing preferences and by adopting patient centered care. We propose a two phase study, in the first phase of the study we will use conjoint analysis to derive patient preference and develop an instrument, in the second phase we will implement a stratified randomized controlled trial to analyze the effects of conjoint analysis (value markers) intervention on treatment choice and outcomes and variation in preference and actual treatment received and its impact on outcomes, and will analyze the effectiveness of active surveillance and active treatment [surgery (RP or RALP), or radiation therapy (EBRT, BT or PT)], on outcomes for low-risk prostate cancer patients. This is a novel study in four ways: (1) assessment of preference using conjoint analysis; (2) development of new tool for assessment of preferences; (3) Comprehensive assessment (HRQoL, and psychological well-being) within and between treatment groups; (4) focus on general population; and (5) rigorous analysis of trust, stress, regrets and depression; Thus, the outcome of this study will facilitate effective clinical decision through patient centered care model so as to achieve optimal outcomes across ethnic and age groups of prostate cancer patients. Also, the results will help understand the effectiveness of prostate cancer care. This study can benefit and aid clinical decision, policy and effective management of prostate cancer.

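### The instrument checks treat unordered specialties and treatments as if they were numeric, and a joint IV comparison of all six treatments would not be identified

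*Combined protocol and SAP*

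**What the plan says.** The opening of the Analysis Plan assigns propensity scores and an IV approach to reducing observed and unobserved bias within each randomized group. The paragraph on instrumental variable analysis then names the instrument: "We will use specialty of the first physician (urologist, urologic oncologist, oncologist, radiation oncologist) who the patient saw during PCa diagnosis as an IV". The list is left open: "We will explore other potential IVs, such as absolute distance between patients residence to the hospital where they will receive care".

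Two checks concern the link between instrument and treatment. The first is "we will use Pearsons correlation coefficient to examine the correlation between IV, primary exposure (treatment) and outcomes". The second is "We will then perform a partial F-test using a linear regression where treatment group is regressed on physician specialty along with patient attributes". The criterion is "For a valid IV, test statistic should be very high", with no number attached.

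The IV paragraph does not say how treatment is coded, which contrasts are to be estimated, or what the second-stage model is. The paragraph just before it, on propensity scores, works with six treatments: "We will use a model relating PCa treatment (RP, RALP, EBRT, PT, BT or AS) to baseline factors". The Design and Subject recruitment sections apply the term 'treatment group' to the same six, with a target of 60 men in each per arm. A coarser grouping appears under Potential Study Benefits, where active surveillance is set beside active treatment, meaning "surgery (RP or RALP), or radiation therapy (EBRT, BT or PT)", in low-risk men. That sentence is not tied to the IV analysis.

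**The concern.** Men are randomized to the conjoint task or usual care, not to a cancer treatment. Comparisons between treatments are therefore observational, and the IV approach is the only method the Analysis Plan names for unobserved bias in them. Two things look wrong.

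- **The checks.** Specialty and treatment are both unordered categories. A Pearson correlation needs a number for each category, and so does a single linear regression with treatment group as the outcome. The plan supplies no numbers. If analysts supply their own, the same data could show a strong or a weak instrument depending on the numbering.
- **The count.** Six treatments give more contrasts than the named instrument can support. If all are estimated together, the equations have no unique solution.

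**Working it through.** The documents give no figure for the IV analysis (no instrument count, F threshold or IV power), so there is no stated result to reproduce first.

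**Inputs from the documents**
- Specialty: 4 categories (IV paragraph), so 4 − 1 = 3 indicators.
- Treatment: 6 categories (propensity-score paragraph; Design; Subject recruitment), so 6 − 1 = 5 contrasts.
- Distance to hospital: one further candidate, functional form not stated.
- Sample: 60 × 2 × 6 = 720 men. The methods are applied within arms, so 720 / 2 = 360 men per analysis.

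**Step 1: order condition.** The number of excluded instruments q must be at least the number of endogenous contrasts k. Patient attributes that also enter the outcome model act as their own instruments and do not add to q.

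| Exposure | k | Instruments | q | Result |
|---|---|---|---|---|
| Six treatments | 5 | specialty | 3 | short by 2 |
| Six treatments | 5 | specialty + linear distance | 3 + 1 = 4 | short by 1 |
| Six treatments | 5 | specialty + linear and quadratic distance | 3 + 2 = 5 | count met |
| Six treatments | 5 | specialty + distance + distance × specialty | 3 + 1 + 3 = 7 | count met |
| Surveillance / surgery / radiation | 2 | specialty | 3 | count met |
| Surveillance vs active treatment | 1 | specialty | 3 | count met |

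Meeting the count is necessary but not sufficient: the extra distance terms must also predict treatment, which nothing in the documents assures. A numerical check on the simulated arm of Step 2 took the rank of the second-stage matrix (constant plus fitted treatment indicators). The rank was 4 of 6 columns with specialty alone, 5 of 6 with linear distance added, and 3 of 3 for the three-group exposure with specialty alone.

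**Step 2: dependence on coding.** This applies if treatment enters as one code from 1 to 6. There are 6! = 720 ways to assign the codes (the match with the sample size is a coincidence). One arm of 360 men, 60 per treatment, was simulated without patient covariates. The specialty mix had to be assumed. The shares below are of each treatment's men by first specialty, in the order listed in the plan.

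| Treatment | Assumed shares |
|---|---|
| AS | 0.45, 0.25, 0.20, 0.10 |
| RP | 0.50, 0.40, 0.05, 0.05 |
| RALP | 0.45, 0.45, 0.05, 0.05 |
| EBRT and BT | 0.25, 0.15, 0.20, 0.40 |
| PT | 0.20, 0.15, 0.20, 0.45 |

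For each numbering, F = [(TSS − RSS)/3] / [RSS/(360 − 4)], from regressing the code on three specialty indicators. Results over the 720 numberings of the same data:
- minimum 0.09 (AS 3, RP 6, RALP 1, EBRT 2, BT 4, PT 5);
- median 4.2;
- maximum 29.6 (AS 3, RP 1, RALP 2, EBRT 6, BT 4, PT 5);
- 77% below 10;
- 34% below 2.63, the 5% critical value.

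**Step 3: indicator coding.** With a yes/no exposure, swapping the labels leaves F unchanged. In the same simulated arm, F was 4.4 for surveillance vs active treatment, 25.1 for surgery vs the rest, and 26.1 for radiation vs the rest. Strength can thus differ by contrast, and a single F would not show that. These values, like those in Step 2, are illustrative only.

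**The case against.** A reader might infer that the IV analysis cannot estimate treatment effects at all, and that its strength test certainly depends on how treatments are numbered. The documents do not support either statement without conditions.

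- The IV paragraph never states a 1-to-6 code. It speaks of the chance of receiving a particular treatment, which fits a yes/no exposure, and Aim 2 models treatment received with a multinomial regression. Analysts who use indicators would avoid the numbering problem in the F-test.
- No second-stage model and no five-contrast target are stated. Aim 3 itself defines improved treatment choice through surveillance versus active treatment in low-risk men, and one such contrast meets the order condition.
- The instrument list is open, and Step 1 shows that richer distance terms could reach the count.
- The simulated F values rest on an invented mix and say nothing about this trial's actual instrument strength.
- The text for Aims 2 to 4 does not call on the IV analysis.

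All of this stands, and it makes the point conditional. It does not remove it. The Pearson check is stated outright and is unsuitable under any reading that keeps four specialties and six treatments. The plan's own use of 'treatment group' means six treatments, and a single regression and test statistic are described, not one per contrast. Taking contrasts singly is not free of cost either. If one treatment is set against all others, specialty may still move men among the others and so reach the outcome by another path. Restricting the analysis to men who had one of two treatments selects on the exposure.

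A reader might also take the Potential Study Benefits sentence as a ready three-group definition for all men. It describes surveillance against active treatment in low-risk men, so a three-group analysis of everyone would be a new choice.

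**Conclusion.** The concern holds in conditional form. The Pearson check is not meaningful for nominal specialty and treatment. If treatment is entered as a numeric code, the strength test depends on an arbitrary numbering. If all six treatments are compared jointly, the named instrument gives 3 for 5 contrasts (4 for 5 with a linear distance term), and the five effects are not identified. The last statement is arithmetic and needs no assumption beyond the six-way joint comparison and the instruments as named. The F range of 0.09 to 29.6 shows only that the numbering can change the answer; its size depends on the assumed mix. With one or two grouped contrasts, specialty alone meets the order condition. The randomized intention-to-treat comparison in Aim 3 does not rely on the IV and is unaffected, so this should be corrected but does not threaten the main comparison.

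**What to change.** Amend the IV paragraph as follows.

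1. Code specialty and treatment as indicator variables, and drop the Pearson correlation.
2. Name the contrasts in advance, with no more contrasts than instruments. Examples are surveillance versus active treatment, or surveillance / surgery / radiation (two contrasts against three specialty indicators).
3. State the second-stage model.
4. Report a first-stage F for each contrast, within each arm, against a stated threshold. Use a conditional F when there is more than one endogenous contrast.
5. State that the IV analysis does not address RP vs RALP, or EBRT vs BT vs PT.
6. For any grouped contrast, state the added assumption that specialty does not affect outcome by shifting men among treatments pooled in one group.

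The cost is analysis wording only; no data collection changes. The downside is that there is no IV estimate within surgery or within radiation, and that the assumption in item 6 must be defended.
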